Primary Endpoint: To compare the incidence of complete wound closure of lyopreserved vs cryopreserved Stravix treated groups at 12 weeks post initial application.

Secondary Endpoints: To evaluate the outcomes noted below between lyopreserved and cryopreserved Stravix.

1. Time to 100% granulation of deep structures (bone, tendon, etc)
2. Duration of NPWT
3. Time to surgical grafting to cover the wound.
4. Time to complete wound closure (complete epithelization with no drainage)
5. Level of infection
6. Quality of Life – SF36, EQ-5D and PROMIS®

Sample Size

For this study, 40 patients from UT Southwestern and Parkland hospitals will complete the study (no cap on screening/enrollment).

Duration of Subject Participation

- Screening: Within 7 days of therapy start
- Treatment period: Up to 12 weeks from therapy start
- Total duration of subject participation: Up to 13 weeks

Screening and Enrollment

Patients who present to the investigator's institution (through clinic admission, direct transfer from another facility, or through the emergency room) may be recruited to participate in the study. No direct marketing for subject recruitment will be done.

Patients approached for study participation will be at least 21 years of age at the time of consent, will undergo wound assessment, and meet all eligibility requirements. Those meeting eligibility criteria for the study will have the study explained to them by the Investigator. An Informed Consent Form will be provided to sign according to Section 11 prior to undergoing any study procedures. Patients will be encouraged to ask questions of the investigators. It will be made clear to the patient that not participating in the study will in no way influence the treatment plan or the relationship with the physician.

There is no cap on the number of subjects that can be screened/enrolled. Additional subjects will continue to be recruited as needed to reach the minimum number of 20 treated per protocol, per arm (40 in total).

Wound Selection

Subjects with only one wound will be included in the study. Subjects with multiple wounds will have each wound measured for volume. The wound with the largest volume meeting all eligibility requirements will be chosen for inclusion in the study as the primary wound. The etiology of the chosen wound, its classification, and if it is a new or recurring, will be documented. All other wounds will be documented as secondary wounds and will be followed throughout the study.

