Randomization

Randomization will be performed using www.randomizer.org. Subjects who meet all inclusion and no exclusion criteria will be randomized in a 1:1 ratio to be treated with NPWT and either lyopreserved Stravix or cryopreserved Stravix. Study staff will use the randomization number labels contained in the envelope. The number will become the subject ID. The research staff will note treatment assignment number on the CRF. ^[17] _[SEP]

Visit Schedule

Study procedures for each phase of study are outlined below. In a later section, details on each study procedure are described, including equipment designation.

Screening

1. Explain purpose and nature of the study and obtain signature on the informed consent document.
2. Screen the subject against protocol inclusion and exclusion criteria, including all pertinent tests

(ex. ABIs), including pregnancy test

3. Complete SF-36, EuroQol 5 dimensions (EQ-5D) and PROMIS®
4. Perform neuropathy assessment
5. Randomize subject if all inclusion and exclusion criteria are met.

Baseline (-within 7 days -after screening)

1. Obtain general medical history and demographic information and social history
2. Complete a physical examination, body weight, height, BMI and vital signs, including measurement of resting heart rate, respiratory rate, and blood pressure while seated.
3. Select target study ulcer
4. Obtain complete history pertinent to DFU disease including duration of the target ulcer, previous and current treatment. Document ulcer classification.
5. Perform debridement and obtain tissue collection (up to 4 tissues and 1 bone if applicable).
6. Collect blood sample at baseline visit (approximately 10mL at each collection) for Ribonucleic Acid (RNA) gene expression.
7. Perform standardized photography and measurement of the primary study wound and, if applicable, secondary study wounds (eKare or available camera with ruler if eKare is not available) pre-debridement. Assess the post-debridement ulcer area (cm^2), perimeter (cm), and greatest depth (cm) using the inSight device (eKare, Fairfax, VA). These values are the baseline measurements for calculating wound closure rate at the two-week run-in visit.
8. Perform hyperspectral imaging of dorsal and plantar aspects of the foot.
9. Collect all relevant concomitant medication (antibiotics, antifungals and other anti-infective therapies)
10. Collect all relevant clinical lab values

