Semmes-Weinstein monofilament evaluation will be performed. We will assess light touch and pressure sensation at five sites on the study foot using a 10-gram monofilaments. We will perform Vibration Perception Threshold VPT; a device that uses vibration to test how well your feet can detect gentle pressure.

Infection Evaluation

This system first divides wounds by whether they are clinically infected on the basis of the presence of purulent secretions or local or systemic signs of inflammation or infection. Infected wounds are further divided into those that are considered to be mild, moderate, or severe, on the basis of the size (especially of any cellulitis) and depth (or level of tissue involved) of the infection and presence of systemic manifestations of infection or metabolic instability [4]. Additionally, the subjects will have the following monitored: temperature, heart rate, respirations and WBC.

Description	International Working Group Infection Severity
no infection: no pus no inflammation	1
2 or more signs of infection (pus, pain, warmth, swelling. cellulitis < 2cm infection limited to the skin or subcutaneous tissue	2

No systemic signs of infection	
2 or more signs of infection (pus, pain, warmth, induration. cellulitis > 2 cm lymphangitis, abscess infection extends to deep fascia, tendon muscle No systemic signs of infection	3
same as 3 with systemic toxicity meets SIRS criteria fever >38C, tachycardia >90, respiration >12, leukocytosis >12,000	4
osteomyelitis	5

Patient Reported Outcomes

The Medical Outcomes Study (MOS) 36-item Short Form (SF-36) is one of the most commonly utilized instruments in assessing diabetic foot disease and provides information on overall physical and mental quality of life. The SF-36 provides a physical component summary (PCS) score as well as a mental component summary (MCS) score, which are derived from eight different sub-scales. The PCS and MCS are standardized so that a score of 50 represents the normative score for the general population, and a higher score is indicative of better HRQOL (20). Excellent correlation has been found between PCS and MCS scores calculated from the SF-36 in patients with diabetic foot disease [5].

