ABI, monofilament, VPT	X														
Wound Assessment, Debridement, Tissue Collection if Applicable+		X				X				X				X	
Stravix Application**		X				**X									
Wound Photography and Measurements, HSI Camera		X	X	X	X	X	X	X	X	X	X	X	X	X	
Offloading		X	X	X	X	X	X	X	X	X	X	X	X		
Adverse Events		X	X	X	X	X	X	X	X	X	X	X	X	X	
Concomitant Medication		X	X	X	X	X	X	X	X	X	X	X	X	X	
Administer SF-36, EuroQol 5 dimensions (EQ-5D) and PROMIS®	X													X	
Subject Stipend		X	X	X	X	X	X	X	X	X	X	X	X	X	
EMR Reference															X

*if subject closes prior to week 12, subject will perform EOS visit and enter the FUP phase

**Stravix should only be removed and replaced if the physician deems it necessary for wound outcomes. If Stravix is not changed until week 4 and at week 4 the wound is not ready for surgical closure, it will be replaced. +Only to be collected if surgical debridement is required.
#will also collect blood if subject develops and recovers from an infection during the study timeframe. Blood will be collected once clinical signs of infection are resolved.

Audits and Inspections

Internal audits are done periodically to assure regulations, guidelines and protocols are adhered to appropriately. Patient binders are reviewed for proper informed consent process documentation, case report forms are compared to the source documents and reviewed for accuracy and an independent review of the inclusion and exclusion criteria using a checklist. Additionally, the use of an auditing and monitoring tool which includes sections on consent, HIPAA, on study/treatment, off treatment/off study and a general section. Weekly meetings occur to go over each study. If there are any issues that arise, they are brought up and discussed at the meeting.

5. Assessment of Efficacy

Effectiveness Endpoints

Primary Endpoint: To compare the incidence of complete wound closure of lyopreserved vs cryopreserved Stravix treated groups at 12 weeks post initial application.

Secondary Endpoints: To evaluate the outcomes noted below between lyopreserved and cryopreserved Stravix.

1. Time to 100% granulation of deep structures (bone, tendon, etc)
2. Duration of NPWT
3. Time to surgical grafting to cover the wound.
4. Time to complete wound closure (complete epithelization with no drainage)
5. Level of infection
6. Quality of Life – SF36, EQD5 and PROMISE

6. Assessment of Safety

Primary Safety Endpoint

Number of index wound related adverse events

7. Statistics

Analysis Plan

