We will summarize study variables as means and standard deviations (SD) for continuous variables and proportions or percentages for categorical variables. Continuous variables will be presented as median, mean \pm standard deviation and dichotomous variables presented as percent. We will use Analysis of Variance (ANOVA) to test for differences in continuous variables. For categorical variables, we will use chi square to compare the proportion of outcomes in each treatment arm with an alpha of 0.05, and we will use Kaplan Meier analysis to compare closure rates of the treatment groups. p-values were reported using the step-up Bonferroni method of Hochberg. We will use an adjusted two-sided analysis with an alpha of 0.05. In the intent to treat analysis, we will use the last observation carried forward to define the clinical outcomes for patients that were lost to follow up.

Tissue samples will be extracted and used for molecular biology analyses. These may include, gene and protein expression of the wound tissue, histological analyses of tissue morphology and pathology, and analyses of bacterial genes to determine levels of infection. All sample analyses will be performed in a de-identified manner and tissue samples WILL NOT be used for genetic sequencing that can be used to deduce the subject's identity.

Sample Size Justification

This is a pilot exploratory study so no sample size justification will be provided.

8. Data Management

Standardized CRFs will be used. Investigators are responsible for the accurate completion and timely submission of the data collected during the trial. All data from the trial will be entered from the CRFs into a central database. Incoming data will be frequently reviewed to identify inconsistent or missing data and any adverse events. Any data issues are to be promptly addressed with the investigator by the Sponsor. Quality assurance procedures will be established to ensure that complete, accurate and timely data are submitted, that protocol requirements are followed and that complications, adverse events and adverse device effects are correctly reported and investigated, as appropriate. Investigators are to maintain all source documents as required by the protocol, including laboratory results, supporting medical records, and signed Informed Consent Forms. The source documents will be used during the regular monitoring visits to verify information from the database against data contained on the completed CRFs.

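### The grade 4 infection row sets its respiratory cut-off at 12, inside ordinary resting rates, and does not say how many systemic criteria are needed, so it can misgrade infection severity

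*Combined protocol and SAP*

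**What the plan says.** Section 4, Infection Evaluation, grades infection from 1 to 5. Grade 3 covers deeper or wider infection and ends with the condition "infection extends to deep fascia, tendon muscle No systemic signs of infection". Grade 4 is "same as 3 with systemic toxicity", followed by the numerical content of that term: "meets SIRS criteria fever >38C, tachycardia >90, respiration >12, leukocytosis >12,000". No unit is printed for respiration; breaths per minute is the natural reading.

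The four items match the monitoring sentence above the table: "the subjects will have the following monitored: temperature, heart rate, respirations and WBC". The Baseline visit describes how the rate is taken: "including measurement of resting heart rate, respiratory rate, and blood pressure while seated". Resting values are therefore the right comparison.

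The rows for grades 2 and 3 state how many local signs are needed (at least two). The grade 4 row gives no count for its four systemic criteria.

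"Level of infection" is a secondary endpoint in the synopsis, in section 4 (Trial Endpoints) and in section 5. For categorical outcomes, section 7 says "we will use chi square to compare the proportion of outcomes in each treatment arm with an alpha of 0.05". No other place in the document gives a different respiratory cut-off, a normal range or a correction.

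**The concern.** The row is meant to pick out systemic toxicity. The temperature and heart-rate items are named as abnormal states (fever, tachycardia), and the white-cell item as leukocytosis. The respiratory item is a bare number that many well people exceed at rest. A criterion met by most subjects whether or not they are systemically ill carries little information.

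The missing count makes the consequence uncertain as well. If one criterion is enough, a moderate infection in a subject breathing normally can be recorded as systemic toxicity. If two are needed, the respiratory item is usually met already and one further sign decides the grade. Two assessors could also read the row differently and grade the same subject differently.

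At stake is the severity distribution in each arm. False grade 4 records would be expected in both arms and would blur any difference in severe infection. With 40 completers, a few misgraded records could change the comparison. Taking vital signs more often would not help, because the fault lies in the threshold.

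**Working it through.** The plan derives no figure here, so there is nothing to reproduce. The check has two steps, and every distributional input is an assumption.

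**Step 1: how often a well adult exceeds 12.** Take the resting rate as Normal with mean m and SD s, so P(rate > 12) = 1 − Φ((12 − m)/s). Rates are counted in whole breaths, so a second version cuts at 12.5: 1 − Φ((12.5 − m)/s).

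| m | s | z at 12 | P, cut at 12 | P, cut at 12.5 |
|---|---|---|---|---|
| 14 | 3 | −0.67 | 0.748 | 0.691 |
| 14 | 2 | −1.00 | 0.841 | 0.773 |
| 16 | 3 | −1.33 | 0.909 | 0.878 |
| 16 | 2 | −2.00 | 0.977 | 0.960 |
| 18 | 3 | −2.00 | 0.977 | 0.967 |
| 18 | 2 | −3.00 | 0.999 | 0.997 |

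For means of 14 to 18 and SDs of 2 to 3, the share is about 75% to 99.9%, or about 69% to 100% with whole-number counts. If the mean were as low as 12, the whole-number share would be 40% to 43%.

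**Step 2: what this does to the grade.** Consider a subject without systemic illness. Let r be the chance of meeting the respiratory item and q the chance of meeting each of the other three, treated as independent.

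- Any one suffices: 1 − (1 − r)(1 − q)³
- At least two: 1 − P(none) − P(exactly one), where P(none) = (1 − r)(1 − q)³ and P(exactly one) = r(1 − q)³ + (1 − r)·3q(1 − q)²
- All four: r·q³

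With r = 0.90 and q = 0.10:

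- Any one: 1 − 0.10 × 0.729 = 0.927
- At least two: 1 − 0.0729 − (0.6561 + 0.0243) = 0.247
- All four: 0.90 × 0.001 = 0.0009

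For comparison, suppose only 2% met the respiratory item (r = 0.02, same q):

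- Any one: 1 − 0.98 × 0.729 = 0.286
- At least two: 1 − 0.7144 − (0.0146 + 0.2381) = 0.033
- All four: 0.02 × 0.001 = 0.00002

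**Sensitivity.** With r from 0.75 to 0.97 and q from 0.05 to 0.15, the any-one reading gives 79% to 98% and the at-least-two reading 11% to 38%. Independence matters for the second. If the other three criteria always occurred together (10% all met, 90% none), the at-least-two result would be 10% whatever r is. Positive correlation among them therefore narrows the gap between 25% and 3%. The any-one result hardly moves: 1 − 0.10 × 0.90 = 0.91.

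**The case against.** The strongest objection is that nothing in the document contradicts the figure of 12. There is no stated normal range and no second cut-off, so the premise rests on general physiology. That is fair. It is why the rate distribution appears above as an assumption with a range, and why no replacement value is offered. It does not rescue the item, which discriminates poorly across the assumed range.

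Second, a reader might infer that grades 3 and 4 merge. The document does not support that as a general statement. It follows only if any single criterion suffices, and the row names a composite without saying so. Temperature, heart rate and white-cell count still separate the grades under the other readings. If all four are needed, grade 4 still requires fever, tachycardia and leukocytosis together.

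Third, a reader might assume that this table is the measure of the secondary endpoint. No section says so. Section 7 also speaks of bacterial gene analyses for levels of infection, and section 4 describes qPCR of tissue samples. The 1-to-5 grade is the likely clinical measure, but not the stated or only one.

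Fourth, exposure is limited. Untreated bone or soft tissue infection is excluded, an infection needing treatment outside the study scope leads to early termination, and the trial is an exploratory pilot. All of this stands, and it limits the weight of the point without removing it.

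Finally, a reader might guess that 12 was carried over from the white-cell figure of 12,000. That is conjecture, and the point does not depend on it.

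**Conclusion.** The point holds as a fault in an outcome definition. A respiratory cut-off of 12 barely discriminates if mean resting rates are around 14 to 18: about 75% to 99.9% of well adults would exceed it. To say that almost every adult exceeds it would be too strong at a mean of 14 and wrong at 12; most is the safer word within the assumed range.

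The effect on grading depends on a rule that the row leaves out. On the illustrative inputs, about 93% of subjects without systemic illness meet the systemic part of grade 4 under an any-one rule and about 25% under a two-criterion rule, against 29% and 3% if the respiratory item were rarely met. Under an all-four rule the effect is negligible. These percentages rest on assumed frequencies and independence; they are not estimates for this population, and they apply only to subjects whose local findings already fit grade 3. The documents give no expected number of such infections.

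The consequence is possible misgrading of clinical infection severity, which likely feeds a secondary endpoint. The primary endpoint of wound closure at 12 weeks is unaffected. The row should be corrected because the repair is cheap and the grade cannot be applied consistently as written.

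**What to change.** 1. Check the respiratory cut-off in the grade 4 row against the SIRS definition that the row names, and reconcile the two. This review does not supply a value.
2. State in the same row how many of the four criteria must be met.
3. Carry both changes into the CRF so that all assessors apply the same rule.
4. Re-grade existing grade 3 and grade 4 records where a respiratory rate was recorded at the time of grading. This may not be possible for all of them: the Schedule of Events lists vital signs only at baseline, and the monitoring sentence under Infection Evaluation names no visits. Records that cannot be re-graded should be identified as such.

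The cost is one table row, a CRF edit and a small re-grading task. The downside is that fewer grade 4 events will probably be recorded.

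### If level of infection is the ordered 1–5 grade, the plan's default chi-square test ignores that order and, under assumed ordered shifts at 20 per arm, gives up roughly 17% to 85% of the rank test's power

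*Combined protocol and SAP*

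**What the plan says.** The synopsis, section 4 (Trial Endpoints) and section 5 all list "Level of infection" as the fifth secondary endpoint. None gives a measure, a time point or a per-subject summary.

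Section 4, Infection Evaluation, has a table headed "International Working Group Infection Severity" with five numbered rows: 1 is no infection, 2 a limited superficial infection, 3 a wider or deeper one, 4 the same as 3 with systemic signs, and 5 osteomyelitis. The text above it describes infection as mild, moderate or severe.

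Section 7, Analysis Plan, names three tools:
- Continuous variables: "We will use Analysis of Variance (ANOVA) to test for differences in continuous variables".
- Categorical variables: "For categorical variables, we will use chi square to compare the proportion of outcomes in each treatment arm with an alpha of 0.05".
- Closure rates: Kaplan-Meier.

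No rank, trend or ordinal method appears. On error control it says "We will use an adjusted two-sided analysis with an alpha of 0.05" and "p-values were reported using the step-up Bonferroni method of Hochberg", without defining the family. The same section plans bacterial-gene assays on tissue as a gauge of infection level. It calls the study an exploratory pilot and offers no sample size justification.

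**The concern.** A five-level grade is a categorical variable, so by the plan's own rule it goes to chi-square. A Pearson test on a 2×5 table spends 4 degrees of freedom on differences of any kind and returns the same p-value if the grades are shuffled. For an endpoint called a level, the natural question is whether one arm sits lower on the scale than the other. With 20 per arm the upper grades will be thinly filled, and the plan names no small-count alternative.

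At stake is the chance of seeing a real shift in infection severity between the two preparations, in a trial too small to spare information. If measure and test stay open, they may also be chosen after the data are seen.

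**Working it through.** **Inputs from the documents.** Chi-square at alpha 0.05, two-sided (section 7); "minimum number of 20 treated per protocol, per arm (40 in total" (section 4, Screening and Enrollment), so 20 per arm; "randomized in a 1:1 ratio" (section 4, Randomization). The plan states no power, effect size or grade distribution, so there is no figure to reproduce.

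**Assumed inputs.** Grade 1–5 percentages in the worse arm: 20/20/20/20/20, 40/20/20/10/10, 50/20/15/10/5, 60/15/10/5/10, 70/12/10/3/5 and 80/8/6/2/4. Proportional odds ratio (OR) 2 to 8. Alpha is left unadjusted because the Hochberg family is undefined; adjustment would lower both powers.

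**Step 1: the shift and the expected counts.** With C the cumulative proportion up to a grade, the better arm has C′ = OR·C / (1 − C + OR·C). For C = 0.5 and OR 4: C′ = 2.0/2.5 = 0.80. The 50% distribution becomes about 80/10.3/5.5/2.9/1.3. Expected count per cell is 20 × the mean of the two arms' proportions: 13.0, 3.0, 2.0, 1.3 and 0.6. Eight of the ten cells fall below 5.

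**Step 2: the price of 4 degrees of freedom.** For 80% power at 0.05 the noncentrality needed is 7.85 on 1 df and 11.94 on 4 df; 11.94/7.85 = 1.52. At the value giving a 1-df test 80% power, the 4-df test has 59.5%; where the 1-df test has 50%, the 4-df test has 30.8%.

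**Step 3: simulation.** 40,000 trials per scenario, Pearson chi-square (empty grades dropped) against tie-corrected Wilcoxon. Power at OR 4, with chi-square's type I error:

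| Grade 1, worse arm | Type I error, chi-square | Chi-square 2×5 | Wilcoxon | Ratio | Chi-square, infected v not |
|---|---|---|---|---|---|
| 20% | 4.7% | 41.5% | 66.0% | 0.63 | 53.0% |
| 40% | 4.1% | 33.0% | 59.7% | 0.55 | 54.5% |
| 50% | 3.4% | 27.1% | 53.2% | 0.51 | 52.7% |
| 60% | 3.0% | 19.3% | 46.4% | 0.42 | 46.8% |
| 70% | 2.2% | 11.9% | 37.1% | 0.32 | 37.1% |
| 80% | 1.3% | 4.0% | 25.3% | 0.16 | 25.7% |

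Wilcoxon's type I error stays at 4.9–5.1%.

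- With 40–60% in grade 1 and OR 2–4, the power ratio is 0.39 to 0.55.
- Smallest loss: even spread, OR 8, 77.0% v 93.2%, ratio 0.83, so 17% lost.
- Largest loss: 80% in grade 1, OR 3, 2.9% v 19.2%, ratio 0.15, so 85% lost.

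**Step 4: in patients.** Per-arm size for 80% power at OR 4, chi-square v Wilcoxon: 44 v 28 (20% grade 1), 58 v 38 (50%), 90 v 58 (70%). The ratios are 1.57, 1.53 and 1.55, in line with Step 2.

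**Step 5: where the result fails.** The last column of the table shows that a two-level chi-square matches Wilcoxon once at least half are grade 1. If the arms are 30/40/20/5/5 and 60/10/10/10/10, a difference in pattern and not an ordered shift, chi-square has 54.3% power and Wilcoxon 19.1%.

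**The case against.** **The link to chi-square is a default reading.** A reader might infer that the plan assigns this endpoint to a 2×5 chi-square. No sentence does so. Section 7 ties bacterial-gene assays to infection level, and section 4 has tissue tested by qPCR for bacterial load; such a measure could be continuous and fall under ANOVA. Even the grade could be scored as a number and sent to ANOVA, which loses less (49% against Wilcoxon's 53% at 50% grade 1, OR 4). This stands: the point is conditional on the grade being the endpoint.

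**A 2×5 table is not specified.** The wording about proportions also fits infected versus not infected, where almost nothing is lost if at least half are grade 1. This stands too, although the plan does not specify that collapse and it discards severity.

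**The size depends on assumptions.** A reader might infer that half the power is lost as a fact of this trial. The documents supply neither distribution nor effect, so only the range can be defended.

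**The scale is not cleanly ordered at the top.** Grade 4 is defined by systemic signs and grade 5 by osteomyelitis, a different dimension, with no rule for subjects who have both. Any rank test inherits that ordering.

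**The grade may not be in the data.** Neither the Schedule of Events nor the visit lists contain an infection-grading step. Section 3 lets infection end participation early, and closed wounds exit early, so follow-up is unequal.

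**Materiality is limited.** Chi-square here is conservative, not invalid, and even Wilcoxon reaches only about 25–66% power at OR 4.

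None of this supplies an ordered method for an ordered grade.

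**Conclusion.** The point holds conditionally. If level of infection means the 1–5 severity grade, the plan's only test for a categorical variable disregards the order across five grades, is conservative when upper grades are sparse, and loses power against an ordered shift. The 17–85% range rests on the assumed distributions, proportional odds with OR 2–8, 20 per arm and unadjusted alpha 0.05; about half is right only for 40–60% in grade 1 and OR 2–4. The documents do not support the flat statements that the endpoint will be tested by a 2×5 chi-square, or that half the power will be lost. Importance is minor to moderate: the endpoint is secondary and the pilot makes no power claim.

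**What to change.** In section 7, Analysis Plan, add text to this effect:

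> Level of infection is the 1–5 grade in the Infection Evaluation section; bacterial-gene results are reported separately. Each subject contributes one grade, the worst recorded after first application through EOS. Subjects terminated early for infection keep the grade at termination. The arms are compared by the tie-corrected Wilcoxon rank-sum test, and counts by grade are tabulated. A sensitivity analysis merges grades 4 and 5. Chi-square is kept for two-level outcomes.

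Worst grade is one workable summary; another single grade per subject would serve if fixed in advance. A proportional-odds model should be optional, since it may be unstable with 40 subjects and sparse upper grades.

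The cost is a short paragraph of analysis text plus recording the grade at the existing visits, with a matching row in the Schedule of Events. The ranking of osteomyelitis above systemic toxicity has to be accepted or tested, which is what the merged-grade analysis is for. A worst grade also covers unequal follow-up, so time under observation should be shown by arm. Power is given up if the arms differ only in pattern; the tabulated counts would still show such a difference.
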